7.7.2.5 Quality of life (EQ-5D Scale)

EQ-5D Index and EQ Visual Analogue Scale (VAS) at baseline and 1 month in the EQ5D CRF will be summarized with number of subjects (n), mean, standard deviation, median, and ranges. The mean, standard deviation, median, and ranges for changes from baseline may also be provided.

[figure not shown]
7.7.2.6 Technical success

Technical success: An evaluation of whether the lung nodule was treated according to the study protocol as determined at the immediate post-procedural timepoint. This is in contrast to procedures in which the protocol could not be executed completely, either for technical reasons or for reasons related to comorbid disease.

In the Procedure CRF, if the question of "Was there technical success, i.e. nodule treated according to protocol?" is checked "YES", it is considered technical success.

The endpoint will be calculated per subject and in the format of p% (x/N), with x being the number of subjects with technical success, and N being the number of all subjects enrolled.

Revision [1.0] Page 12 of 15

7.7.2.7 Technique efficacy

Technique efficacy: An evaluation of whether the lung nodule was effectively ablated. Evaluates whether complete ablation of the nodule was achieved as evidenced by imaging follow-up 1-month post-procedure (including a window of 20-40 days post-procedure).

In the FUP CRF, if the question of "Based on imaging, was complete ablation of the nodule achieved?" is checked "YES", it is considered that the lung nodule was effectively ablated.

The endpoint will be calculated per subject and in the format of p% (x/N), with x being the number of subjects whose complete ablation of the nodule achieved, and N being the number of subjects with performed follow-up imaging.

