## 8.2. Subject Enrollment

Up to 30 subjects will be enrolled at up to 3 sites in up to 3 regions. The minimum and maximum number of subjects to be included at each site are not prespecified since the study is not statistically powered.

For the purpose of this clinical study investigational plan, the point of enrollment is defined as the insertion of the Emprint™ Ablation Catheter Kit with Thermosphere™ Technology into the EWC.

Subjects will be approached to obtain written informed consent prior to any institution non-standard-of-care assessments or study-specific data being collected. During the index procedure imaging, nodule eligibility criteria will be re-confirmed. Any patients with nodules no longer meeting eligibility criteria will not be enrolled. Subjects who provide study consent but then are determined to be ineligible prior to the insertion of the ablation catheter will be considered screen failures and documented as such in the database.

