### 9. Study Procedures

Following confirmation of eligibility and informed consent, subjects with inoperable lung nodules will undergo an ablation procedure using a bronchoscopic approach. A target nodule will be identified on a pre-procedure CBCT scan. Nodule localization will be aided by ENB using the superDimension™ navigation system. Once localized, if no suitable bronchus sign leads to the proposed area to ablate, access to the region may be obtained using the CrossCountry™ Transbronchial Access Tool. Once ablation region access has been achieved, the ablation catheter will be placed inside the EWC and will be unsheathed inside the target nodule. Correct positioning will be verified using CBCT and the nodule will then be ablated. AEs related to Emprint™ Ablation Catheter Kit with Thermosphere™ Technology, accessory devices, or study procedures will be captured and reported until the 1-month follow-up visit.

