# 9.2. Subject Screening

A baseline visit will be performed within 30 days prior to the scheduled procedure to assess study eligibility. During the index procedure imaging, nodule eligibility criteria will be re-confirmed. Consented subjects will be considered for the study if they meet specified inclusion criteria and none of the exclusion criteria. The criteria for enrollment must be followed explicitly.

Subjects who provide study consent, but then are determined to be ineligible prior to the start of the ablation portion of the procedure will be considered screen failures and will not require additional study follow-up visits. The reason for the Screen Failure will be clearly documented on the applicable electronic case report forms (eCRFs). Screen failures will not be counted towards the number of study subjects.

MDT18010ILSBA

Version 4.0

26-SEP-2019

Page 24 of 50

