#### 9.11. Subject Withdrawal or Discontinuation

Subjects may voluntarily withdraw from the study if they no longer wish to have their study-related information used. Additionally, the Principal Investigators may withdraw or choose not to enroll subjects if they feel they do not meet the CIP defined inclusion and exclusion criteria or if it is in the best medical interest of the subjects in question.

In cases of voluntary subject withdrawal, all data collected from the time of informed consent to the time of voluntary withdrawal may be used. The General Data Protection Regulation (GDPR) process will be followed as applicable per country regulations. Withdrawn subjects will not be replaced. Enrollment will continue as per CIP definitions up to the predefined maximum number of subjects.

All subjects will be followed per institutional standard of care after any withdrawal, discontinuation, or completion of the study follow-ups.

The reason for study exit of all enrolled subjects will be documented on the applicable electronic case report form (eCRF). In the event the subject withdraws consent during the study, the date of withdrawal will be documented. If the study investigator voluntarily removes a subject from further study participation, supporting documentation must be in place for the rationale and date of removal. Every attempt will be made to contact subjects who are noncompliant. Subjects will be considered lost to follow-up once the following steps have been taken:

- Three phone calls should be made to the subject. Each attempt should be clearly documented in the source documents and the response or lack thereof should be captured.
- If there is no response to the phone calls, then a certified/registered letter should be written to the subject. A copy of the letter should be retained in the subject's source document.
- After a period of one week following completion of the above actions, the subject will be considered lost to follow-up. The sponsor should be notified and the Study Exit form should be completed.

MDT18010ILSBA

Version 4.0 26-SEP-2019

Page 30 of 50

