7.1 Study Subjects

7.1.1 Disposition of Subjects

After being informed of the nature of the study, the subject will sign a written informed consent form (ICF) that has been approved by the appropriate Institutional Review Board (IRB) or Ethics Committee (EC) of the respective clinical site. The point of enrollment is defined as the insertion of the Emprint™ Ablation Catheter Kit with Thermosphere™ Technology into the EWC, rather than at the time of informed consent.

Subjects will be evaluated at baseline, procedure and 1 month, as detailed in Table 1 below. All study data will be collected on the appropriate subject eCRFs.

[figure not shown]
Table 1. Table of Assessments

	Baseline (Day -30 to Day 0)	During the Procedure and Immediately Post- Procedure	1-Month Follow- up (20 to 40 Days Post- Procedure)
Subject demographics	Х		
Medical history (Lung Diagnoses, Previous Lung procedures, Lung function tests, etc.)	x		
Eligibility assessment	Х	Х	
Nodule characteristics		Х	
Procedural information		Х	
Adverse event assessment		Х	Х
Imaging	X*	Х	Х
Concomitant medications	х	Х	Х
Quality of life survey (EQ-5D)	Х		Х
Bronchoscopic Ablation Patient Pain and Satisfaction Survey			Х

^{*}Standard-of-care CT scan performed prior to consent.

Revision [1.0]

Page 7 of 15

Subject disposition (e.g., number completing the study, number lost-to-follow-up) will be summarized with frequency tables. For subjects exiting the study, the reason for termination will be presented.

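### Technical success is conditional on catheter insertion: failures to reach the nodule cannot enter its denominator, and no per-attempt rate is planned beside it

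*SAP*

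**What the plan says.** **Technical success.** SAP 7.7.2.6 contrasts success with "procedures in which the protocol could not be executed completely, either for technical reasons or for reasons related to comorbid disease". The rate is per subject, with "N being the number of all subjects enrolled".

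**Enrolment.** Protocol 8.2 and SAP 7.1.2 set it at insertion of the catheter kit into the EWC. Protocol 14.1 declares this openly as a departure from enrolment at consent. Protocol 9 gives the order of steps: "Once ablation region access has been achieved, the ablation catheter will be placed inside the EWC".

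**Subjects who never enrol.** Protocol 8.2 says that consented subjects "determined to be ineligible prior to the insertion of the ablation catheter will be considered screen failures". Protocol 9.2 has "determined to be ineligible prior to the start of the ablation portion of the procedure will be considered screen failures", and keeps screen failures out of the subject count. Protocol 9.11 says: "The reason for study exit of all enrolled subjects will be documented". SAP 7.1.1 says: "Subject disposition (e.g., number completing the study, number lost-to-follow-up) will be summarized with frequency tables".

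**Safety endpoints.** SAP 7.7 uses a different N for these: everyone who had the index ENB procedure. It plans an exact 95% interval for the primary endpoint only.

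**Technique efficacy.** SAP 7.7.2.7 divides complete ablations by imaged subjects, with "N being the number of subjects with performed follow-up imaging". The endpoint's imaging window is 20 to 40 days after the procedure.

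**The concern.** The technical success definition names technical reasons as a way to fail. Being unable to navigate to the nodule, or to gain access to it, is such a reason. But a subject becomes part of N only when the catheter goes into the EWC, and that happens once access has been gained. One kind of failure that the endpoint describes is thus removed from the denominator before it can be counted.

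Protocol 6 says that the study characterizes the bronchoscopic ablation procedure performed with this kit. A reader planning a later study may take the reported percentage as the chance that an attempted procedure succeeds. It is the chance of success given that the catheter was inserted. No planned output for this endpoint lets the reader move from one to the other.

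**Working it through.** The plan states no expected rate, precision or power for either endpoint, so there is no figure of its own to reproduce.

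**Inputs from the documents.** Maximum enrolment is 30 (SAP 6). The approximate minimum is 20 (Protocol 3, Statistics). Intervals below use the exact binomial method that SAP 7.7 plans for the primary endpoint.

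**Inputs assumed.** The number of access failures before insertion (a) and the number of enrolled subjects without follow-up imaging (m). The documents give neither.

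**1. Direction.** Let x be technical successes and E enrolled subjects. The planned rate is x/E. The per-attempt rate is x/(E + a). Since a ≥ 0, x/(E + a) ≤ x/E, and for x > 0 the two are equal only when a = 0. This follows from the order of steps and needs no assumed count.

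**2. Illustrative size.** The exact limits are the 2.5% quantile of Beta(x, n − x + 1) and the 97.5% quantile of Beta(x + 1, n − x). For x = n the lower limit is 0.025^(1/n), so for 30/30 it is 0.025^(1/30) = 0.884. Suppose every enrolled subject is a success:

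| Enrolled | a | Planned rate | Per-attempt rate |
|---|---|---|---|
| 30 | 1 | 30/30 = 100% (88.4-100) | 30/31 = 96.8% (83.3-99.9) |
| 30 | 2 | 30/30 = 100% (88.4-100) | 30/32 = 93.8% (79.2-99.2) |
| 30 | 3 | 30/30 = 100% (88.4-100) | 30/33 = 90.9% (75.7-98.1) |
| 20 | 1 | 20/20 = 100% (83.2-100) | 20/21 = 95.2% (76.2-99.9) |
| 20 | 2 | 20/20 = 100% (83.2-100) | 20/22 = 90.9% (70.8-98.9) |

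**3. Can a be recovered afterwards?** Not reliably. Both screen-failure definitions turn on ineligibility. Neither says how to record an eligible subject whose nodule could not be reached. Exit reasons are required for enrolled subjects, and the disposition examples are completion and loss to follow-up. The two cut-offs also differ. If the ablation portion is taken to start after insertion, a subject found ineligible between the two moments is enrolled under Protocol 8.2 and a screen failure under 9.2. That changes E itself.

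**4. SAP 7.7 against SAP 7.1.2.** Read literally, N for the safety endpoints (subjects with an index ENB) can include subjects in whom no catheter was inserted. The analysis set in 7.1.2 cannot. Protocol 11.1 collects adverse events only from enrolment, so on the literal reading those extra subjects enlarge N but cannot contribute an event.

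**5. Technique efficacy (minor).** With x complete ablations, m un-imaged and E enrolled, the bounds are x/E and (x + m)/E, a width of m/E. For m = 1, 2 or 3 of 30 the width is 3.3, 6.7 or 10.0 points. Example with m = 3: the planned rate is 24/27 = 88.9% (70.8-97.6), and the bounds are 24/30 = 80.0% (61.4-92.3) and 27/30 = 90.0% (73.5-97.9).

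**The case against.** **The study is about the catheter kit.** Navigation relies on the superDimension system and access may use the CrossCountry tool, which are separate products. Conditioning on insertion fits a device question, and the enrolment point is disclosed. Failures after insertion, such as in unsheathing, positioning or energy delivery, all stay in N. This stands. It is why the current rate should be kept and labelled rather than replaced.

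**A reader might infer that the plan contains no per-attempt denominator at all.** The documents do not support that. The N in SAP 7.7 is close to one, although it is stated for the safety endpoints only and does not match SAP 7.1.2.

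**Non-enrolled subjects are not wholly undocumented.** Protocol 9.2 requires the reason for each screen failure on the eCRF, and Protocol 9.4 foresees consented subjects who prove unsuitable for the ablation procedure. This narrows the gap. It does not settle where an eligible subject with an unreachable nodule belongs.

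**A reader might infer that the technique efficacy rate is biased upward.** That is possible but not shown. The imaged-only rule is stated openly and is allowed by SAP 7.1.2. The bounds follow from x/N and the enrolled count. Uncollected data points are generally deviations (Protocol 15.2), and deviations are tabulated (SAP 7.10). This half is a convenience to the reader.

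**The shifts are hypothetical, and the intervals overlap widely.** True. Only the direction is established.

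**Conclusion.** The point holds for technical success. By construction the planned rate can only equal or exceed the per-attempt rate, because failures to reach the nodule occur before a subject can enter N. This rests on the order of steps in Protocol 9 and the enrolment definition, with no assumed count. The size is unknown. At 30 enrolled, one to three assumed access failures would put the per-attempt rate at 96.8% to 90.9% against a planned 100%.

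The mismatch between SAP 7.7 and 7.1.2, and that between Protocol 8.2 and 9.2, are real and decide who is counted. For technique efficacy only an optional addition is warranted.

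Both endpoints are secondary and descriptive, the study is not powered, and Protocol 7.10 says that it does not specifically evaluate efficacy claims. This is a cheap improvement to how the rates are read, not an error that overturns a conclusion.

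**What to change.** **SAP 7.7.2.6.** Keep the current rate and label it 'conditional on catheter insertion'. Add a row, with an exact 95% CI, in which N is consented subjects whose index ENB for ablation was started, excluding those stopped only because the nodule no longer met eligibility. Show the number without insertion and the reasons.

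**SAP 7.7 and 7.1.2.** Reconcile the safety-endpoint N with the enrolled analysis set, bearing in mind that adverse events are collected only from enrolment.

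**Protocol 8.2 and 9.2, at the next amendment.** Reconcile the two screen-failure cut-offs, and state how an eligible subject whose nodule was not reached is recorded.

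**Optional, SAP 7.7.2.7.** Beside the imaged-only rate, show the all-enrolled lower and upper bounds with the number and reasons un-imaged. Call them sensitivity bounds, so that they are not mistaken for the imputation that SAP 7.3 and Protocol 13 rule out. State how scans outside days 20-40 are handled, in line with the endpoint's own window; they should not stay in the main rate by default.

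**Cost.** A few table rows, possibly one added eCRF reason item for subjects who never enrolled, and a Protocol wording change that needs the approvals in Protocol 15.6. The added rate may be less favourable than the current one.

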7.8 Safety Evaluation

7.8.1 Definitions of Adverse Events

7.8.1.1 Adverse Event

An AE is any untoward medical occurrence, unintended disease or injury, or untoward clinical signs (including abnormal laboratory findings) in subjects, users or other persons, whether or not related to the investigational medical device.

NOTE 1: This definition includes events related to the investigational medical device or the comparator.

NOTE 2: This definition includes events related to the procedures involved.

NOTE 3: For users or other persons, this definition is restricted to events related to investigational medical devices.

7.8.1.2 Serious Adverse Event

A Serious Adverse Event (SAE) is an AE that has

- 1. Led to death,
- 2. Led to serious deterioration in the health of the subject, that either resulted in
 - a. A life-threatening illness or injury, or
 - b. A permanent impairment of a body structure or a body function, or
 - c. In-patient or prolonged hospitalization, or

Revision [1.0] Page 13 of 15 Form

d. Medical or surgical intervention to prevent life-threatening illness or injury or permanent impairment to a body structure or a body function.

NOTE 1: This includes device deficiencies that might have led to an SAE if a) suitable action had not been taken or b) intervention had not been made or c) if circumstances had been less fortunate. These are handled under the SAE reporting system.

NOTE 2: Planned hospitalization for a pre-existing condition, or a procedure required by the clinical investigational plan, without serious deterioration in health, is not considered an SAE.

7.8.1.3 Adverse Device Effect

An Adverse Device Effect (ADE) is an AE related to the use of the investigational medical device (the Emprint™ Ablation Catheter Kit with Thermosphere™ Technology).

NOTE 1: This definition includes AEs resulting from insufficient or inadequate instructions for use, deployment, implantation, installation, or operation, or any malfunction of the investigational medical device.

NOTE 2: This definition includes any event resulting from use error or from intentional misuse of the investigational medical device.

7.8.1.4 Unanticipated Serious Adverse Device Effect

[figure not shown]
An unanticipated serious adverse device effect (USADE) is a serious adverse event related to the study device which by its nature, incidence, severity or outcome has not been identified in the current version of the Risk Management Report.

7.8.1.5 Adverse Event Relationship Classification

The following definitions will be used to assess the relationship of the AE to the investigational medical device (the Emprint™ Ablation Catheter Kit with Thermosphere™ Technology), accessory devices, or study procedures:

- Not related: Relationship to the device or procedures can be excluded
- Unlikely: The relationship with the use of the device seems not relevant and/or the event can be reasonably explained by another cause, but additional information may be obtained.
- Possible: The relationship with the use of the investigational device is weak but cannot be ruled out completely. Alternative causes are also possible (e.g. an underlying or

Revision [1.0] Page 14 of 15

concurrent illness/ clinical condition or/and an effect of another device, drug or treatment). Cases were relatedness cannot be assessed or no information has been obtained should also be classified as possible.

• Probable: The relationship with the use of the investigational device seems relevant and/or the event cannot reasonably be explained by another cause, but additional information may be obtained.

For the AE relatedness reporting, the degree of causality's term "not related" will be considered as not related to the device or procedures, and terms "unlikely", "possible" or "probable" will be considered as related to the device or procedures.

7.8.2 Reporting of Adverse Events

All summaries of adverse events will be based on events that occurred during the study. Adverse event reporting is per Medical Monitor adjudication for those that require Medical Monitor adjudication, and the remaining events will be per site reported data.

Adverse events will be mapped to preferred terms (i.e. Dictionary-Derived Term) and Body System or Organ Class using the Medical Dictionary for Regulatory Activities (MedDRA) coding dictionary. The number and percentage of subjects experiencing adverse events will be summarized by system organ class and preferred term.

7.9 Device Deficiencies Analyses

A device deficiency is an inadequacy of a medical device related to its identity, quality, durability, reliability, safety or performance, such as malfunction, misuse or use error and inadequate labeling.

Device deficiencies will be summarized in frequency measures by device type and device deficiency category. For the device deficiencies that result in SAEs, a detailed subject listing will be provided including subject number, device type, device deficiency category, deficiency description, deficiency time, device deficiency outcome, SAE description, action taken, and event outcome.

7.10 Protocol Deviation

A protocol deviation is defined as any divergence from the study protocol. The total number of protocol deviations and total number of subjects with deviations will be provided by deviation type for all enrolled subjects.

[NAVABLATE] Statistical Analysis Plan		Form
Revision [1.0] Page 15 of 15		Medtronic

8. Validation Requirements

Level II validations (i.e. the peer reviewer reviews the code; where appropriate, performs manual calculations or simple programming checks to verify the output) will be performed for analysis outputs.
